## **2.5 Secondary Objectives**

- Overall Survival at 30 days is a key secondary endpoint.
- Improvement in inflammatory markers associated with cytokine storm (Ferritin, C-Reactive Protein (CRP), d-dimer, white blood cell count)
- Cumulative incidence of grade 3 and 4 adverse events during hospitalization
- Cumulative incidence of serious adverse events during hospitalization
- Duration of hospitalization
- Duration of ventilation
- Ventilator free days (reintubations or death within 28 days will result in zero ascribed time off ventilator prior to reintubation)
- Improvement in oxygenation or paO2/FIO2 ratio

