## 7. STATISTICAL CONSIDERATIONS

### 7.1 Sample Size Considerations

This study will be performed with two cohorts 1) severe COVID-19 infection and 2) moderate COVID-19 infection (as defined in inclusion criteria).

The effect of the intervention will be evaluated in each cohort separately. A total of 32 patients will be enrolled in each cohort with a 3:1 allocation ratio (24 Etoposide and 8 control per cohort). Assuming a 30% response rate in the control group for the primary outcome of a 2 point improvement in respiratory status on an 8 point scale at Day 14, we can detect a 50% increase in response in the Etoposide group (80% response rate in the Etoposide group) with a 2-sided  $\alpha$  of 0.05 and 80% power. While this study is not powered to detect a statistically significant difference in outcome, it will provide initial evidence of efficacy if improvement in response is observed.

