## 7.2 Statistical Analysis

Tabulations overall, and by treatment group, will be produced for appropriate demographic, baseline, efficacy, and safety parameters, with number and percentages reported for categorical variables and the mean, median, standard deviation, and range for continuous variables. All analyses will be performed at an  $\alpha=0.05$  level using SAS v.4.

Efficacy analyses will be performed in an intention-to-treat (ITT) population consisting of all patients randomized. The difference in ordinal scale improvement rates between treatment arms will be calculated with a 95% confidence interval and formally compared using Fisher's Exact Test. For secondary analysis of the primary endpoint, logistic models individually adjusted for age, diabetes, chronic lung disease/moderate or severe asthma, immunocompromise, liver disease, heart disease/hypertension, smoking and obesity (BMI  $> 40$ ), residence in long-term care facility, will also be examined with odds ratios and 95% confidence intervals reported.

The analysis of secondary time to event endpoints including survival at 30 days, duration of hospitalization, duration of ventilation and ventilator free days, will be compared between treatment arms based on a log-rank test. The median will be estimated with a 95% CI for each treatment arm using the Kaplan-Meier method. Cox proportional Hazards models adjusted individually for age, diabetes, chronic lung disease/moderate or severe asthma, immunocompromise, liver disease, heart disease/hypertension, smoking and obesity (BMI  $> 40$ ), residence in long-term care facility, will also be examined with odds ratios and 95% confidence intervals reported. Changes in inflammatory markers and in oxygenation or  $\text{paO}_2/\text{FIO}_2$  ratio, based on available recorded measurements, will be compared between treatment arms using a two sample t-test, or a Wilcoxon Rank Sum test, as appropriate. Incidence of grade 3 or 4 AEs and serious AEs will be compared using Fisher's Exact test.

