## 8.2 Response Definitions

8-Point Ordinal Scale:

- 8 - Death;
- 7 - Ventilation in addition to extracorporeal membrane oxygen (ECMO), continuous renal replacement therapy (CRRT), or need for vasopressors (dopamine  $\geq 5$   $\mu$ g/kg/min OR epinephrine  $\geq 0.1$   $\mu$ g/kg/min OR norepinephrine  $\geq 0.1$   $\mu$ g/kg/min);
- 6 - Intubation and mechanical ventilation;
- 5 - Non-invasive mechanical ventilation (NIV) or high-flow oxygen;
- 4 - Hospitalized, requiring oxygen by mask or nasal prongs;
- 3 - Hospitalization without oxygen supplementation;
- 2 - Discharged from hospital either to home with supplemental oxygen OR to inpatient rehabilitation/skilled nursing facility (+/- supplemental oxygen);
- 1 - Discharged to home without supplemental oxygen

When calculating Ventilator Free days, reintubations or re-hospitalizations or death occurring in the first 28 days should result in zero ascribed to time off the ventilator prior to reintubation

When calculating days of hospitalization, re-hospitalization or death occurring in the first 28 days should result in zero ascribed to time out of the hospital prior to readmission.

When determining days of supplemental oxygen use and need for supplemental oxygen, the patient will only be considered to no longer need supplemental oxygen if a room air saturation is  $\geq 90\%$  after five minutes of rest.

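### Section 7.2 analyses ventilator-free days by time-to-event methods although 2.5 and 8.2 define it as a zero-penalised 28-day score; no event or censoring rule is given, so the effect of deaths depends on how the score is coded

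*Combined protocol and SAP*

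**What the plan says.** Section 7.2 opens the relevant paragraph with "The analysis of secondary time to event endpoints including survival at 30 days" and carries the list through to "duration of ventilation and ventilator free days, will be compared between treatment arms based on a log-rank test". For the same group it then plans "The median will be estimated with a 95% CI for each treatment arm using the Kaplan-Meier method" and "Cox proportional Hazards models adjusted individually for age, diabetes" and further covariates.

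The endpoint is described in two other places. Section 2.5 lists "Ventilator free days (reintubations or death within 28 days will result in zero ascribed time off ventilator prior to reintubation". Section 8.2 repeats the rule, adds re-hospitalization, and says that "death occurring in the first 28 days should result in zero ascribed to time off the ventilator prior to reintubation".

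For endpoints that are not times to an event (inflammatory markers and oxygenation), 7.2 already has a different comparison: these "will be compared between treatment arms using a two sample t-test, or a Wilcoxon Rank Sum test, as appropriate". VFD is not assigned to it.

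Nowhere does the plan say what the event is for VFD, how a value of zero enters the risk set, whether a death is an event or a censored observation, or which direction of the hazard ratio is favourable.

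**The concern.** A log-rank test needs an event and a rule for censoring. VFD has neither. It is a number of days, known in full at day 28, with a cluster at zero made up of the worst outcomes. To run the planned test the analyst has to choose a coding, and the obvious choices treat deaths differently:

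- If every value is an event, all the zeros fall at the first time point. A log-rank test gives that point no more weight per event than any other, so the contrast between dying and surviving is mixed with differences among survivors.
- If zeros are censored at day 0, those patients leave before the first event and the penalty for death disappears.

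Direction is a further trap. For duration of ventilation, named beside VFD in the same sentence, an earlier event is good. For VFD an earlier event is bad. That is a matter of labelling, but it invites a misread hazard ratio.

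What is at stake is the purpose of the zero rule, which is to stop a treatment from looking better on ventilator time because more of its patients died. In an open-label trial, the coding should not be left until the data are in hand.

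**Working it through.** The plan states no power, event count or expected value for VFD, so there is no figure of its own to reproduce. The 80% power in 7.1 belongs to the primary endpoint and has no bearing here. The arm sizes come from 7.1: "3:1 allocation ratio (24 Etoposide and 8 control per cohort". All mortality, zero-fraction and extubation inputs below are assumptions, because the documents give none.

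**1. Worked example.** Assume 12 of 24 deaths on etoposide and 2 of 8 on control, all scored 0. Survivors come off on days 8, 10, 12, 14, 16 and 18 (two per day on etoposide, one per day on control), so VFD = 28 − day = 20, 18, 16, 14, 12, 10. Survivors are distributed identically; only mortality differs. Mean VFD is 2 × 90/24 = 7.5 vs 90/8 = 11.25; the median is 5 vs 13.

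*Rank-sum, zeros kept as values.* U for etoposide = 12×2 + ½(12×2) + ½(12×6) = 24 + 12 + 36 = 72, against an expected 24×8/2 = 96. The tie-corrected variance is (24×8/12) × [33 − (2730 + 144)/(32×31)] = 16 × 30.10 = 481.6, SD 21.95. With continuity correction |z| = 23.5/21.95 = 1.07, p = 0.28, in favour of control.

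*Log-rank, every value an event.* At VFD = 0 there are 14 events among 32 at risk, 24 of them on etoposide: expected 14 × 24/32 = 10.5, observed 12. At each later value two of three events are on etoposide and two-thirds of the risk set is on etoposide, so observed equals expected. In total O − E = 24 − 22.5 = 1.5. The variance is 1.524 + 0.588 + 0.571 + 0.545 + 0.500 + 0.400 + 0 = 4.13, so z = 1.5/2.03 = 0.74. The direction is right if an early event is read as bad, but the signal is weaker.

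*Log-rank, zeros censored at day 0.* The first term drops out: O = 12, E = 12, z = 0.00. The doubled mortality leaves no trace.

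**2. Simulation at the planned size.** 24 vs 8 patients, a point mass at zero plus a uniform positive part, each test at |z| > 1.96 (8,000 runs; re-runs agree within simulation error). Positive VFD is uniform over 1-22 days unless stated.

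| Assumed scenario (etoposide vs control) | Rank-sum | Log-rank, all events | Log-rank, zeros censored |
|---|---|---|---|
| Zeros 60% vs 35%: harm detected | about 20% | 10-11% | 2-3% |
| Same zeros, survivors 6-24 vs 1-19 days: test favours etoposide | about 0.2% | about 2% | about 36% |
| Zeros 25% vs 60%: benefit detected | 33% | 29% | 7% |

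**3. Does the loss come only from small numbers?** With 240 vs 80 patients, mortality 50% vs 25% and the same extubation distribution among survivors, rejection is 95.7% by rank-sum, 58.7% by log-rank with all events, and 5.0% with zeros censored. The dilution and the hiding persist in a large sample.

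**The case against.** Several points against this carry weight.

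**Coding.** A reader might infer that the planned analysis necessarily hides or reverses the effect of deaths. The documents do not support that, because 7.2 specifies no coding. If every value is an event, the direction is kept, and the false-favour rate in the adverse scenario is about 2%, near the nominal 2.5% in that direction. Hiding and reversal of the score need zeros censored at day 0. No section proposes that, and it sits badly with the intention-to-treat population in 7.2 and with the zero that 8.2 says to ascribe. A reversal can also be produced by analysing time to end of ventilation with death as the event (z = +0.52 towards etoposide in the worked example), but that is closer to duration of ventilation than to VFD.

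**The zero rule.** A reader might take the whole score to be zero after any reintubation. Sections 2.5 and 8.2 zero only the time off the ventilator before the reintubation, so later ventilator-free time can still count. Both texts are unclear for a death without reintubation. The cluster at zero remains, from deaths and from patients never extubated.

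**False positives.** Under no effect, the all-events log-rank favours etoposide in about 4% of trials against a nominal 2.5%. That is not evidence about VFD: with no zeros at all the rate is still about 4%. It is a small-sample asymmetry of log-rank at 24:8.

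**Reach.** A reader might conclude that excess deaths would go unseen. They would not. Thirty-day survival is the key secondary endpoint with its own analysis, and the Section 6 calendar records mortality at Days 14, 30 and 60. For a real benefit, the all-events coding loses little power (29% vs 33%).

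What remains is that the stated method does not fit the stated endpoint, and the rule needed to carry it out is missing.

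**Conclusion.** The point stands as a mismatch between 7.2 and the definitions in 2.5 and 8.2, worth correcting before analysis. The mismatch is read directly from the text and needs no assumption.

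Its size does need assumptions. At 24 vs 8, the most defensible time-to-event coding roughly halves the chance of detecting harm on VFD (from about 20% to 10-11%). The least defensible leaves 2-3%, and favours the more lethal arm in about 36% of trials when its survivors also come off the ventilator sooner. These figures depend on the assumed zero fractions and day ranges, and power is low under every method. They show how far the answer can move with an unstated choice; they do not predict this trial's result.

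VFD is one secondary endpoint. The primary comparison by Fisher's exact test and the 30-day survival analysis are untouched. The matter bears most on cohort 1, whose patients are intubated at entry.

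**What to change.** In 7.2, remove VFD from the list of time-to-event endpoints and drop Kaplan-Meier and Cox for it. Compare the scored VFD (0 to 28, zeros kept as values) between arms by the Wilcoxon rank-sum test that 7.2 already names for other endpoints. Give a difference with a 95% confidence interval, for example Hodges-Lehmann, and report the proportion with zero VFD in each arm so that the contribution of deaths is visible.

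For the score to be computed one way only, 2.5 and 8.2 should also agree on whether re-hospitalization counts, and should state the value for a death without reintubation.

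The cost is one sentence in 7.2 and a small alignment of the two definitions. No new data are needed, and sample size and the primary analysis do not change.

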## **2.3 Number of patients**

- 32 patients in each cohort with 3:1 allocation ratio (24 etoposide and 8 control per cohort)
- 64 patients total

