## **4.3 Randomization**

Randomization will be performed using a 3:1 allocation ratio using a block size of 4 separately in each cohort.

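### With 24 vs 8 patients per cohort, the log-rank test in 7.2 splits its 5% error unevenly between benefit and harm, and nothing is planned for sparse logistic and Cox models

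*Combined protocol and SAP*

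**What the plan says.** Section 2.3 plans "32 patients in each cohort with 3:1 allocation ratio (24 etoposide and 8 control per cohort"), and 7.1 repeats "24 Etoposide and 8 control per cohort". Section 4.3 randomizes with a "3:1 allocation ratio using a block size of 4 separately in each cohort", so a fully accrued cohort has exactly 8 controls. Under 7.1, "The effect of the intervention will be evaluated in each cohort separately", so the 8 controls are never pooled.

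In 7.2 the primary endpoint, grade 3 or 4 adverse events and serious adverse events are compared with Fisher's exact test. Four time-to-event endpoints (30-day survival, duration of hospitalization, duration of ventilation, ventilator-free days) get a log-rank test: each "will be compared between treatment arms based on a log-rank test". Section 2.5 makes 30-day survival the key secondary endpoint. Section 7.2 also plans "logistic models individually adjusted for age, diabetes, chronic lung disease/moderate or severe asthma, immunocompromise, liver disease" and further covariates, nine in all, and Cox models with the same nine. That is 9 logistic + 4 × 9 = 36 Cox = 45 adjusted models per cohort.

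For the log-rank tests and the models, no exact, permutation or penalized method is named, and nothing is said about zero cells or separation. Expected mortality and covariate prevalence are not stated.

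**The concern.** The log-rank p-value and maximum-likelihood estimates rest on large-sample theory, and the control arm has 8 patients. When controls are a quarter of those at risk, the control death count is skewed. An excess of control deaths has a long tail, while a deficit stops at zero. A symmetric normal reference then rejects too readily in one direction and too rarely in the other. For death, the favoured direction is benefit from a cytotoxic drug.

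The models have a related problem. If no control patient responds, the treatment odds ratio is infinite. If all carriers of a rare covariate have the same outcome, that covariate's coefficient is infinite, and the fit in effect drops those carriers instead of adjusting for them. Without a rule set in advance, the response to such results would be chosen after seeing the data.

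**Working it through.** **Inputs from the documents.** 24 vs 8 per cohort (2.3, 4.3, 7.1); two-sided α "of 0.05 and 80% power" and "Assuming a 30% response rate in the control group", against 80% on etoposide (7.1); follow-up to Day 30 for survival (2.5). **Assumed, because not stated:** 30-day mortality 10-80%, exponential death times, covariate prevalence 5-60%, covariates unrelated to outcome.

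**The plan's own figure.** The unpooled two-proportion z-test gives 0.5/√(0.3×0.7/8 + 0.8×0.2/24) = 0.5/0.1814 = 2.756, and Φ(2.756 − 1.96) = 78.7%. This is close to the stated 80% and confirms the inputs. It concerns the primary endpoint; the plan gives no figure for the log-rank test or the models.

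**Log-rank, by hand.** Let p be the fraction of those at risk who are controls at each death. Then z = (control deaths − Σp)/√Σp(1−p).

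- Benefit side: two deaths, both controls. Σp = 8/32 + 7/31 = 0.476, the variance is 0.362, and z = 1.524/0.602 = 2.53. The test rejects. The exact chance of this split is C(8,2)/C(32,2) = 28/496 = 5.6%.
- Harm side: D deaths, all on etoposide, p = 8/(32−i) for i = 0 to D−1. At D = 9, z = −2.594/√1.840 = −1.91; at D = 10, z = −2.942/√2.067 = −2.05. With fewer than 10 deaths, a harm finding is impossible. At 20% mortality, 32 × 0.2 = 6.4 deaths are expected.

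**Log-rank, simulated.** 400,000 cohorts per setting, no true effect (nominal 2.5 / 2.5 / 5.0):

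| Mortality | Favours etoposide | Harm | Total |
|---|---|---|---|
| 10% | 3.1% | 0.0% | 3.1% |
| 20% | 3.8% | 0.2% | 4.0% |
| 30% | 3.8% | 1.0% | 4.8% |
| 40% | 3.8% | 1.5% | 5.3% |
| 50% | 3.8% | 1.7% | 5.5% |
| 60% | 4.0% | 1.7% | 5.6% |
| 80% | 4.2% | 1.9% | 6.1% |

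Smaller simulations, with deaths recorded by whole day, widen the 20-60% range to 3.3-4.4% and about 0.2-2.2% (lowest single estimate 0.12%, at 20% mortality). With 16 vs 16 the split is about even, so the 3:1 allocation is the cause.

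**Permutation log-rank, 2.5% in each tail.** The favourable tail falls to 2.2-2.8%. The harm tail is 0.05, 0.6, 1.3, 2.4 and 2.6% at 20, 30, 40, 50 and 60% mortality. A permutation test on the absolute statistic does not cure the imbalance: 3.9% vs 0.2% at 20% mortality, 3.6% vs 1.4% at 40%.

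**Detection of a real effect** (mortality, etoposide vs control):

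| Scenario | Asymptotic | Equal-tailed permutation |
|---|---|---|
| Benefit, 25% vs 60% | 50-52% | 41-44% |
| Harm, 60% vs 25% | about 35% | about 40% |
| Harm, 40% vs 10% | 24-26% | 19-21% |
| Harm, 30% vs 10% | 6-7% | about 4% |

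The low-mortality loss has a simple source. With 10 deaths, none in controls, the exact tail probability is C(22,8)/C(32,8) = 319,770/10,518,300 = 3.0%, above 2.5%. With 11 it is 203,490/10,518,300 = 1.9%. The permutation test therefore needs 11 such deaths where the asymptotic test needs 10.

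**Treatment odds ratio.** No control responds with probability 0.7^8 = 5.8% at the plan's rate. Adding 0.3^8 (all controls respond) and 0.8^24 = 0.5% (all etoposide patients respond) gives 6.2% for 30% vs 80%. Adjusted for one binary covariate, it is non-finite in about 5-11% of cohorts. If the control rate were 20%, 0.8^8 = 17%; if 10%, 0.9^8 = 43%. The same arithmetic gives the chance of no control deaths, and so of no finite Cox estimate for survival: 17% at 20% mortality and 6% at 30%.

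**Covariate coefficients, 30% control response.** Some coefficient is non-finite in 52-58% of cohorts at 5% prevalence, 36-45% at 10%, 13-20% at 20% and 6-11% at 40%. In addition, the covariate is absent altogether in 0.95^32 = 19% or 0.9^32 = 3% of cohorts. Across eight binary-covariate logistic models, at least one fails (separated or absent) in 93-96% of cohorts with a low-prevalence mix and 25-48% with a higher one. The treatment odds ratio itself fails in at least one model in 7-20%.

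**Firth, example.** For 0/8 vs 12/24 responders, maximum likelihood has no finite odds ratio; Firth gives (12.5/12.5)/(0.5/8.5) = 17.0.

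**The case against.** A reader might infer that the log-rank test fails here. It does not: the plan states a two-sided α of 0.05 and promises nothing per tail, and the total error is 3.1-6.1%. That part of the objection stands. It does not remove the point, because a significant survival result is read by its direction.

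A reader might also infer that the treatment odds ratio often does not exist. At the plan's own 30% control response that is untrue. The frequent failures concern covariate coefficients at prevalences the documents do not give, and when only the covariate is separated the treatment estimate usually stays finite.

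Nor is the survival p-value the trial's safeguard against harm. Death is a serious adverse event (9.2), serious adverse events are compared by Fisher's exact test (7.2), and deaths go to the Medical Monitor within 24 hours (10.2). The affected analyses are secondary, and 7.1 says the study is not powered for a significant difference. This limits the weight of the point. It does not explain why sparse results have no planned handling while 7.2 still tests everything at 0.05.

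The strongest objection is to the remedy: at low mortality the permutation test detects harm less often. This is correct, and lower mortality is plausible in the non-intubated cohort 2. The loss must be stated with the change.

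**Conclusion.** The point holds as a modest, inexpensive improvement to secondary analyses. For 30-day survival at 24 vs 8, the planned test puts about 3.3-4.4% of its error in the tail favouring etoposide and 0.2-2.2% in the harm tail, at assumed mortality of 20-60% with exponential death times. For discharge or extubation the same skew counts against etoposide. The treatment odds ratio is non-finite in about 5-11% of cohorts at 30% control response, more often if that rate is lower. Coefficients of uncommon covariates are separated in roughly 36-45% of cohorts at 10% prevalence and 52-58% at 5%; these prevalences are assumptions. The documents do not support a claim that the methods of 7.2 fail as a whole, or that the primary comparison is affected.

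**What to change.** In 7.2:

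1. Take the log-rank p-value for survival from the permutation distribution, with 2.5% in each tail. State explicitly that it is not based on the absolute statistic, which leaves the imbalance in place.
2. Fit the adjusted logistic and Cox models with Firth's penalized likelihood and profile-likelihood intervals (the FIRTH option in SAS PROC LOGISTIC and PROC PHREG). Omit a covariate that is absent from a cohort, since no method can then estimate its effect.

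The cost is SAP wording and a few lines of code. The statistical price should be disclosed: lower apparent power for benefit, because the excess error in that tail is removed; better harm detection at higher mortality; and poorer harm detection at low mortality. At 20% mortality the harm tail stays near zero under either test, because there are too few deaths for 8 controls to show a deficit.

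### For 30-day survival, the key secondary endpoint, Section 7.2 names a Kaplan-Meier median and mislabelled Cox ratios, but no Day 30 survival estimate or between-arm difference with a confidence interval

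*Combined protocol and SAP*

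**What the plan says.** Section 2.5 lists the secondary objectives and singles one out: "Overall Survival at 30 days is a key secondary endpoint".

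Section 7.2 analyses it in one block with duration of hospitalization, duration of ventilation and ventilator-free days. All four endpoints get the same three items:

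- a log-rank comparison of the arms;
- a Kaplan-Meier summary: "The median will be estimated with a 95% CI for each treatment arm using the Kaplan-Meier method";
- models introduced as "Cox proportional Hazards models adjusted individually for age" and then each further covariate in turn, which "will also be examined with odds ratios and 95% confidence intervals reported".

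Section 7.2 also opens with a general promise to tabulate efficacy parameters by treatment group, with counts and percentages for categorical variables. For the primary endpoint, and only there, it plans a between-arm difference in rates with a 95% confidence interval.

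Section 2.3 fixes the size: "32 patients in each cohort with 3:1 allocation ratio (24 etoposide and 8 control per cohort". Section 7.1 adds: "The effect of the intervention will be evaluated in each cohort separately". Each survival analysis therefore compares 24 patients with 8.

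A footnote to the Section 6 calendar schedules mortality at Days 14, 30 and 60. The last paragraph of Section 4.1 follows standard-of-care patients only to death or discharge.

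**The concern.** The endpoint is a landmark quantity, the probability of being alive at Day 30. A Kaplan-Meier median answers a different question, the time by which half the arm has died, and has no value if fewer than half die during the period analysed. It suits hospital stay or time on a ventilator. It suits 30-day survival only when mortality is high.

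The Cox sentence adds a second difficulty. A Cox model estimates a hazard ratio, and a reader who sees an odds ratio cannot tell whether the label or the model was changed.

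Section 7.1 says the trial is not powered for statistical significance and is meant to give initial evidence. Its value on mortality therefore lies in estimates with their precision. As written, the named survival outputs could be an unreached median, a low-powered p-value and a ratio with the wrong name. The only direct figure for Day 30 would be a bare percentage from a general table.

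**Working it through.** **The plan's own figures.** None concerns survival. The phrase "of 0.05 and 80% power" and the 30% control rate ("Assuming a 30% response rate in the control group for the primary outcome") belong to the ordinal-scale primary endpoint. For 30% against 80% with 8 and 24 patients, SE = √(0.3×0.7/8 + 0.8×0.2/24) = 0.181, 0.5/0.181 = 2.76, and Φ(2.76 − 1.96) = 78.7%. This unpooled normal approximation comes close to the stated 80%. The planned Fisher's exact test gives 67.9%, which is a separate matter. No expected mortality, event count or survival power is given, so mortality below is an assumption and is shown as a range.

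**Inputs.** n = 24 and n = 8 (Sections 2.3 and 7.1). Observation stops at Day 30, with no censoring before then.

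**Step 1: is the median reached by Day 30?** Counting exactly half dead as reached, the probability is P(X ≥ n/2) with X ~ Binomial(n, m), where m is 30-day mortality. That is X ≥ 4 of 8 or X ≥ 12 of 24. The last column is the product of the two, with m the same in both arms.

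| Assumed m | 8 controls | 24 etoposide | Both arms |
|---|---|---|---|
| 20% | 5.6% | 0.1% | <0.1% |
| 30% | 19.4% | 3.1% | 0.6% |
| 40% | 40.6% | 21.3% | 8.6% |
| 50% | 63.7% | 58.1% | 37.0% |
| 60% | 82.6% | 88.6% | 73.2% |
| 70% | 94.2% | 98.8% | 93.1% |

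**Step 2: is the upper 95% limit of the median reached by Day 30?** This requires the upper confidence limit of S(30) to lie below 0.5. On the log-log scale with Greenwood variance S(1 − S)/n, that takes at least 7 deaths of 8 or 17 of 24.

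| Assumed m | 8 controls | 24 etoposide |
|---|---|---|
| 40% | 0.9% | 0.2% |
| 50% | 3.5% | 3.2% |
| 60% | 10.6% | 19.2% |
| 70% | 25.5% | 56.5% |

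**Step 3: does the label matter?** Take 30-day mortality of 50% in control and 30% on etoposide. The odds ratio is (0.3/0.7)/(0.5/0.5) = 0.43. Under proportional hazards the hazard ratio is ln(0.7)/ln(0.5) = 0.51. These are different numbers for the same data.

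**Step 4: how much can the log-rank test carry?** Simulating the same 50% against 30%, with exponential survival, 8 against 24 patients and censoring at Day 30, gives power of about 22% to 23% at two-sided 0.05.

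**Step 5: is the missing estimate feasible at this size?** Suppose, for illustration, 17 of 24 etoposide and 4 of 8 control patients are alive at Day 30. Survival is 70.8% (exact 95% CI 48.9% to 87.4%) and 50.0% (15.7% to 84.3%). The difference is 20.8 points. The Wilson limits are 50.8% to 85.1% and 21.5% to 78.5%, so the Newcombe interval runs from 20.8 − √(20.0² + 28.5²) = −14.0 to 20.8 + √(14.3² + 28.5²) = 52.7 points. It is wide, but it is always available and shows what the trial can say about mortality.

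**The case against.** A reader might infer that no estimate of 30-day survival by arm is planned at all. The documents do not support that. Alive or dead at Day 30 is a categorical efficacy parameter, Section 6 schedules its collection, and the general tabulation in Section 7.2 can cover it. What is missing is an interval for that percentage and a between-arm difference with an interval.

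A reader might also infer that the median will usually not be reached, whatever happens. That depends on a rate the documents do not give. It holds at about 40% mortality or less and fails at about 50% or more, which cannot be excluded in the intubated first cohort. Section 7.2 also does not say that survival is censored at Day 30. If deaths to Day 60 were used, the median would be reached more often than Step 1 shows.

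Three further defences have some weight. The median sentence serves four endpoints and is natural for the durations. The odds-ratio phrase repeats the end of the logistic-model sentence one paragraph earlier, so it is probably a slip for a correctly named model. And the Cox models would supply an effect with an interval, so the p-value would not stand alone.

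None of this supplies the landmark estimate. Section 7.2 writes out a difference with an interval for the primary endpoint and does not do so for the key secondary one.

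**Conclusion.** The point holds in this limited form. For 30-day survival, the plan names a summary that is not the quantity in Section 2.5 and an effect measure that the named model does not produce. It specifies neither a Day 30 survival estimate with an interval nor a between-arm difference with one.

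The size depends on unknown mortality. At 30%, both arms reach a median in 0.6% of trials; at 60%, in 73.2%. Even at 50%, where each arm more often than not reaches a median, its upper limit is reached by Day 30 only about 3% of the time. These figures assume observation to Day 30, no earlier censoring and, for the both-arms column, equal mortality in the arms.

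The wrong effect label does not depend on mortality, but it is a correction of wording. The endpoint is secondary, and the sample size and primary analysis are untouched. The change should be made, but the point does not threaten the trial.

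**What to change.** Change Section 7.2 as follows:

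1. For 30-day survival, report the Day 30 survival proportion in each arm and the difference between arms, each with a small-sample 95% confidence interval. Use the Kaplan-Meier estimate, or the binomial proportion if vital status at Day 30 is complete. Name the interval methods in advance, for example Clopper-Pearson for each arm and Newcombe for the difference in the binomial case.
2. Keep the log-rank test as supportive.
3. Limit the Kaplan-Meier median to the duration endpoints.
4. Replace odds ratios with hazard ratios for the Cox models.

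Also reconcile Section 4.1, where control follow-up ends at death or discharge, with the Day 30 mortality assessment in Section 6. If controls were censored at discharge, those leaving hospital would drop out because they had recovered. Neither a complete-data proportion nor the usual Kaplan-Meier assumption of uninformative censoring would then hold for that arm.

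The cost is wording in the analysis section and one clarification of follow-up. No patients or visits are added beyond the mortality assessments already scheduled.
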